## Protocol

**Background:** Patients receiving a new pacemaker or defibrillator are currently given Bupivacaine, Lidocaine, or a mixture of the two for local anesthetic treatment (in addition to general anesthesia). The choice of local anesthetic to be used during surgery is based primarily on the differences in time for the anesthetic to take effect and duration thereafter. Lidocaine typically works in less than 1 minute and lasts approximately 45 minutes. Bupivacaine works within 2 to 3 minutes and lasts 4 to 6 hours. Lidocaine is often preferable due to its shorter time of effectiveness. However, its relatively short duration may translate into a higher use of intravenous (IV) narcotics for pain management during postoperative care – particularly within the first hour following emergence from general anesthesia. Therefore it is conceivable that these patients would have higher levels of pain as well as higher cost of care related to cost of narcotics and caregiver time required to administer them.

**Objectives:** The goal of the proposed study is to investigate the relationships between treatment with lidocaine or a mixture of lidocaine and Bupivacaine and pain, consequent narcotic treatment, and patient movement during anesthesia while adjusting for other clinical and/or demographic factors in consecutive subjects who undergo arrhythmia surgery at Baylor Heart and Vascular Institute over several months.

****This study will focus primarily on assessing the relationship between local anesthetic choice and postoperative pain for patients who receive a new pacemaker or defibrillator. The primary outcome of interest is: pain as measured by a standardized and validated scale, the Visual Analog Scale (VAS) at 3 time points: prior to surgery, once awakened from surgery, 4 hours after, and 4-24 hours after. The secondary outcomes of interest are: IV narcotic use (including dosages and strength of narcotic) within 1 hour after the patient emerges from general anesthesia and patient movement during the insertion of pacemaker or defibrillator. Data source: All data for the proposed investigation will be abstracted from the patient charts included in the study cohort.

**Study Design:** The proposed investigation is a randomized trial comparing the efficacy of two standard local anesthetic treatments in terms of postoperative pain and narcotic use following pacemaker or defibrillator insertion. Standard local anesthetic choice will be classified as Lidocaine (a standardized dose of 10 cc 1% solution) or a combination of Bupivacaine and Lidocaine (a standardized dose of 6 cc 1% Lidocaine mixed with 4 cc 0.25% Bupivacaine solution). Both solutions are clear with a total volume of 10 cc. The BHVH pharmacy will draw up the appropriate treatment, rendering the surgeon administering the local anesthetic blinded to the identity of the local anesthetic. Volume administered as well as other clinical and demographic data will be obtained for each patient. Pain will be measured using the VAS (a standardized and validated scale) at 3 time points: prior to surgery, once awakened from surgery, 4 hours after, and 4-24 hours after. The type, number, and dose of narcotics will be collected up to 24 hours after patient awakens from surgery. The study cohort will comprise all consenting patients who undergo new pacemaker or defibrillator insertion and consent to have data collected regarding the insertion of a pacemaker/defibrillator device at Baylor Heart and Vascular

(Dallas, TX) between 11/03/2008 and 08/30/2012, approximately 350 patients. Additional Study Procedures are attached after the protocol.

**Inclusion Criteria:** Patients consenting to routine data collection in Apollo at Baylor Jack and Jane Hamilton Heart and Vascular Hospital, at least 18 years of age, and receiving only: ICD implant, single chambered pacemaker implant, or dual chambered pacemaker implant, for whom either Lidocaine or Bupivacaine is not contraindicated.

**Exclusion Criteria:** Patients not consenting to routine data collection in Apollo at Baylor Jack and Jane Hamilton Heart and Vascular Hospital; and/or under 18 years of age; and/or receiving procedures other than: ICD implant, single chambered pacemaker implant, or dual chambered pacemaker implant; and/or Lidocaine or Bupivacaine is contraindicated.

**Risks:** Risks incurred as a result of administering lidocaine or lidocaine / Bupivacaine mixtures for this study will be no different than the risks incurred via administration of either treatment as a result of standard care in pacemaker / defibrillator insertion. These risks include: CNS depression, CNS excitement, cardiac arrhythmias, allergic reaction, and trouble breathing (allergic reaction, low blood pressure, difficulty breathing, fast heart rate, slow heart rate, feeling light headed, tremors, seizure, chest pain, weak pulse, nausea, vomiting, anxiety, speech problems and headache).

**Potential Benefits:** It is possible that one treatment may result in diminished pain post-surgery. This would result in diminished pain for those participants assigned to that specific treatment group. This research may benefit individuals in society by revealing a more cost effective treatment with less pain incurred after implementation of pacemaker/defibrillator devices.

**Risk to Benefit Analysis:** Patients receiving a pacemaker or defibrillator are currently given Bupivacaine, Lidocaine, or a mixture of the two for local anesthetic treatment (in addition to general anesthesia). The choice of local anesthetic to be used during surgery is based primarily on the differences in time for the anesthetic to take effect and duration thereafter. Lidocaine typically works in less than 1 minute and lasts approximately 45 minutes. Bupivacaine works within 2 to 3 minutes and lasts 4 to 6 hours. Lidocaine is often preferable due to its shorter time of effectiveness. However, its relatively short duration may translate into a higher use of narcotics for pain management during postoperative care – particularly within the first hour following emergence from general anesthesia. Therefore it is conceivable that these patients would have higher levels of pain, higher cost of care related to cost of narcotics, and higher cost of caregiver time required to administer them. Either treatment is standard for these procedures, so no additional risk will be incurred by assigning treatment to either Lidocaine or Bupivacaine/Lidocaine mixture.

**Payment/ Compensation/ Subject Costs:** The research subjects will not receive a stipend for participation in the study. There will be no cost to the subjects.

### **Confidentiality**

**Data Storage:** An appropriate database will be created and managed in compliance with HIPAA regulations. Data will be stored safely in a secure environment, and maintenance for back-up purposes will be performed on a routine basis.

**Research Subject Privacy:** Patients will be approached discretely and privately by the study coordinator on location at Baylor Heart and Vascular Hospital prior to their procedure. The discretion of the study coordinator will be used to judge if privacy (from both medical personnel and other persons in the hospital) is ensured during the consent process. The patient will be informed that they can stop the consent process at anytime if they feel their privacy is being compromised. No information will be collected directly from the patient after this point. Patient will be informed that participating / not participating in this study will in no way affect their care and that they are in no way obligated or expected to participate. If the patient agrees to participate, they will be taken through the informed consent process. Upon data acquisition, study identifiers will be encrypted to protect patients' privacy and meet HIPAA regulations, and data will be stored in a secured database while periodic back-up will protect against catastrophic data loss. All hard copy material (summary printouts) will be stored by the principal investigator in locked file cabinets and the disks, diskettes, and other removable storage media files will be safely stored as per HIPAA regulations. The ability to decode the study identifier will be restricted to the principal investigator.

**Study Procedures:**

**Defining potential participants**

Timing: **1 day prior to surgery:**

**On-Site Study Coordinator:**

- On-Site Study Coordinator will access the EP's schedules via MediTech one day prior to surgery. Those patients receiving any of the following may be considered for inclusion in the study:
  - BiVD (CRT)
  - ICD
  - Pacemaker
- On-Site Study Coordinator will contact Electrophysiologist to gain permission to approach patient.

**WebEx Login info:**

**Web address:** <http://sphinxanesthesia.webexone.com>

**Login Name:**

**Login Password:**

**Consent and Randomization**

Timing: **Day of surgery – Prior to procedure immediately following consent.**

Location: **4th Floor BHVH.**

**On-Site Study Coordinator:**

- On-Site Study Coordinator will approach patient the day of procedure, *prior to procedure* in patient room to consent patient.
- On-Site Study Coordinator will retain a signed copy of the consent document. The study participant will also be provided a copy of the consent document.
- On-Site Study Coordinator will determine randomization assignment of each participant the day of procedure after having consented the participant. Randomization will occur as follows:
  - Within the randomization notebook, the section corresponding to the appropriate EP will be selected.
  - Within this section, the appropriate procedure subsection (based upon the gender of the participant) will be selected.
  - Within this section, the subsection representing the patient's procedure type will be selected.
  - In first available slot on the procedure type section, the On-Site Study Coordinator will enter the patient's name, MRN and social security number in the appropriate location.
    - Treatment assignment number will be listed to the right of SSN.
    - The treatment assignment number correlates to an envelope with the treatment assignment sealed within to be brought to the BHVH pharmacy, **only to be opened by the pharmacy staff.**
- On-Site Study Coordinator will attach a study participation letter onto the patient's chart prior to EP entry into the surgical room.

On-Site Study Coordinator will inform nursing staff of patient enrollment into study ( on 3rd floor BHVH ).
---

**Treatment Preparation**

Timing: **Day of surgery – Prior to EP entering EP suite.**

Location: **3rd Floor BHVH**

**EP nursing staff:**

- EP nursing staff will look at patient chart to identify if study participation letter is present and notify the electrophysiologist.
- EP nursing staff will provide the electrophysiologist with the pre-drawn syringe.
- EP nurse will report “local anesthetic” and dosage in the patient’s chart as per usual procedure.

**Surgical Procedure**

Timing: **Day of surgery - During surgical procedure / device implantation**

Location: **3rd floor BHVH**

**EP Nursing staff:**

- Please follow standard protocol for recording/measuring pre-operative pain.

**Anesthesiologist:**

- You will have no real responsibilities for this trial; however, we do ask that you **standardize the anesthesia protocol with fentanyl and propofol** (using anything else such as midazolam, sufentanyl, etomidate, pentothal, ketorolac and local anesthetics like mepivacaine could disqualify the patient).
- Dosing should be based on individual patient factors and your judgment.
- **If for any reason you must deviate from this protocol, please notify On-Site Study Coordinator and/or research coordinator.**

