**On-Site Study Coordinator:**

- On-Site Study Coordinator will check EP lab records to determine local anesthetic given to patient.
- On-Site Study Coordinator will abstract chart information onto case report form.
- Adverse events will be determined from patient charts and reported within 7 days.
- All forms will be forwarded to the research coordinator.

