**Research coordinator:**

- Research coordinator will verify randomization number received correct study medication.
- BHVH data will be queried to verify all patients are discharged post-surgery (disposition type, disposition date, and discharge date will be queried). If they are not discharged this may constitute serious adverse event (SAE) and research nurse or coordinator will report to IRB immediately (within 24 hours).

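### The anesthesiologist instructions allow a patient to be disqualified after randomisation for intra-operative drug use, and the plan does not say who decides or whether such patients are analysed

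*Combined protocol and SAP*

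**What the plan says.** Assignment comes first. Under Consent and Randomization the timing is "Prior to procedure immediately following consent", and the on-site coordinator "will determine randomization assignment of each participant the day of procedure after having consented the participant".

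The disqualification wording comes later, in the anesthesiologist's instructions under Surgical Procedure, timed as "Day of surgery - During surgical procedure / device implantation". Those instructions ask for a standard regimen of fentanyl and propofol and add that "using anything else such as midazolam, sufentanyl, etomidate, pentothal, ketorolac and local anesthetics like mepivacaine could disqualify the patient". The drug list is illustrative and the consequence is conditional. The only action required after a deviation is to notify a coordinator.

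The nearest thing to a statement of who is in the study is in Study Design (item 4): "The study cohort will comprise all consenting patients who undergo new pacemaker or defibrillator insertion". The Exclusion Criteria (item 6) cover consent, age, procedure type and contraindication to the study drugs. They do not mention drugs given during surgery. No section defines disqualification, says who decides it, or names an analysis set.

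**The concern.** A patient removed for something that happens during surgery is removed after the arm is fixed. The reason for removal may depend on how well the assigned local anesthetic worked. Item 3 names "patient movement during the insertion of pacemaker or defibrillator" as a secondary outcome, and another agent may be given in response to movement or to an inadequate block. If such patients are dropped, and the rate or the type of patient dropped differs between arms, those who remain are no longer comparable as randomised.

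Because the wording leaves the consequence open, each removal can also be settled case by case after assignment. The outcome data should still exist, since they are abstracted from patient charts. The gap therefore concerns inclusion in the analysis, not follow-up.

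**Working it through.** **Sequence.** Consent, then randomisation, then surgery with possible use of another agent, then possible disqualification. The two timing lines settle this order, so any disqualification on this ground is post-randomisation.

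**The two statements side by side.** Item 4 takes in every consenting patient who has the implant. The anesthesiologist's instructions say that some of those same patients could be disqualified. Neither refers to the other, and item 6 does not reconcile them. If item 4 describes enrolment, nothing states the analysis set. If it describes the analysis set, it conflicts with the disqualification wording.

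**Size if removed patients are dropped.** The plan gives no figure to reproduce. Its only usable input is about 350 patients (item 4). The rest is assumed: 1:1 allocation (350/2 = 175 per arm), VAS SD 25 mm, correlation ρ = 0.5 between intra-operative response and later pain, no true difference, two-sided test at 0.05.

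Suppose an arm loses the fraction p of patients with the worst intra-operative response. Let z be the standard normal upper-p point, φ the normal density, and λ = φ(z)/(1 − p). Then:

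- fall in the arm's mean VAS = ρ × SD × λ
- variance among those left = SD² × [1 − ρ²λ(z + λ)]
- bias b = difference between the two arms' falls
- type I error = Φ(−1.96 − b/SE) + 1 − Φ(1.96 − b/SE)

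Worked case, 15% v 5% removed:

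- 15% arm: z = 1.036, φ = 0.2332, λ = 0.2332/0.85 = 0.2743; fall = 0.5 × 25 × 0.2743 = 3.43 mm; variance 568.8; 175 × 0.85 = 148.75 patients left
- 5% arm: z = 1.645, φ = 0.1031, λ = 0.1031/0.95 = 0.1086; fall = 1.36 mm; variance 595.3; 175 × 0.95 = 166.25 patients left
- b = 3.43 − 1.36 = 2.07 mm; SE = √(568.8/148.75 + 595.3/166.25) = 2.72 mm; type I error 0.119

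| Removed (arm v arm) | Pattern | Bias, mm | SE, mm | Type I error |
|---|---|---|---|---|
| 2% v 1% | all response-driven | 0.28 | 2.66 | 0.051 |
| 6% v 5% | all response-driven | 0.23 | 2.68 | 0.051 |
| 16% v 10% | all response-driven | 1.18 | 2.75 | 0.072 |
| 15% v 5% | all response-driven | 2.07 | 2.72 | 0.119 |
| 16% v 10% | half response-driven | 0.75 | 2.78 | 0.058 |
| 15% v 5% | half response-driven | 1.28 | 2.75 | 0.075 |
| 5% v 5% | response-driven in one arm, unrelated in the other | 1.36 | 2.71 | 0.079 |

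In the half-driven rows, the unrelated half is removed at random first. At 15% v 5% this leaves the worst 8.1% v 2.6% of the remainder to be removed by response.

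**Sensitivity to ρ, all removals response-driven.** For ρ = 0.3 and 0.7, the bias is 0.14 and 0.32 mm at 6% v 5%, and 1.24 and 2.90 mm at 15% v 5% (type I error 0.073 and 0.198).

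**Simulation check** (20,000 trials, ρ = 0.5). It gave 2.05 mm and 0.116 for 15% v 5%, and 0.22 mm and 0.049 for 6% v 5%. With 10% removed from each arm in the same way it gave 0.02 mm and 0.049.

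The bias is zero when removal is unrelated to outcome, or when both the rate and the type of patient removed are the same in each arm. Equal rates alone are not enough, as the last table row shows. Narcotic use and movement were not quantified.

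**The case against.** The wording is a conditional aside in a request to the anesthesiologist, not a formal exclusion rule. A reader might infer that the plan directs these patients to be dropped. It does not: notification is the only required action, item 6 is silent, and item 4 on its face includes these patients. That stands, and the point is limited to a removal the plan permits without defining it.

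The mechanism is also weaker than it first looks. The plan allows two responses to movement or an inadequate block that carry no disqualification. Fentanyl and propofol dosing is left to the anesthesiologist's judgment, and the surgeon's instructions allow more local anesthetic, with documentation and notification. Both make response-driven use of another agent less necessary. Other use may be chosen before the block or for unrelated reasons. This limits the risk without removing it.

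A reader might further infer that removals would be decided by staff who know the arm, because coordinators are notified of deviations and also have drug-checking duties ("On-Site Study Coordinator will check EP lab records to determine local anesthetic given to patient"; "Research coordinator will verify randomization number received correct study medication"). The documents do not support that. They never say that coordinators decide; those checks take place after surgery; and the nurse's chart entry may read only as a local anesthetic and its dose. What can be said is that no decision-maker is named.

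Lastly, every numerical input except the approximate sample size is assumed, and the largest figures need a three-fold difference between arms with every removal response-driven. That is right, and it is why the size is given as a range and not as an estimate.

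**Conclusion.** The point holds in limited form. The plan contains a discretionary post-randomisation removal that is undefined, has no named decision-maker and has no stated consequence for the analysis. The cohort sentence neither mentions it nor cancels it. This is more than missing detail, because using the rule as written can bias the randomised comparison.

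Whether it would do so, in which direction and by how much cannot be derived from the documents. At low removal rates of the same kind in both arms the effect is negligible (type I error about 0.05). It reaches about 0.12 only in the worst-case pattern at 15% v 5% with correlation 0.5. This is a cheap improvement, not a demonstrated error.

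**What to change.** In the anesthesiologist's instructions, replace the words about disqualifying the patient with: *will be recorded as a protocol deviation; the patient remains in the study*. The anesthesia request itself is unchanged.

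In Study Design (item 4), add: *The primary analysis includes all randomised patients with outcome data, in the arm assigned, regardless of other agents or supplemental local anesthetic.*

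Report deviations by arm. Keep any deviation-free subset, defined blind to arm, as a sensitivity analysis only, since it is itself selected after randomisation.

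The cost is one replaced phrase, one added sentence and one extra table. There are two real downsides. Keeping patients with deviations dilutes the contrast between the two local anesthetics somewhat. Removing the warning also weakens the stated incentive to follow the standardised anesthesia request. Outcomes already come from charts, so keeping these patients should need little new data collection.

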**Surgeon:**

- You will administer local anesthetic as given to you by the EP nursing staff.
- If for any reason you are required to give more local anesthetic, you may do so, but it is important that the supplemental administration be documented in the Apollo report.
- **Please notify On-Site Study Coordinator or research coordinator if you are required to administer more local anesthetic.**

**Data abstraction and adverse event monitoring**

**Timing: Post-surgery**

**EP Nursing Staff:**

- Please follow standard protocol for recording/measuring post-operative pain.

**On-Site Study Coordinator:**

- On-Site Study Coordinator will check EP lab records to determine local anesthetic given to patient.
- On-Site Study Coordinator will abstract chart information onto case report form.
- Adverse events will be determined from patient charts and reported within 7 days.
- All forms will be forwarded to the research coordinator.

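### The on-site coordinator, who enrolls, randomizes and abstracts, is told to find out which local anesthetic was given: a masking risk that a short rewording removes

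*Combined protocol and SAP*

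**What the plan says.** All places are in the combined protocol and SAP.

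- **Data abstraction and adverse event monitoring, On-Site Study Coordinator.** The first bullet reads: "On-Site Study Coordinator will check EP lab records to determine local anesthetic given to patient". The second gives the same role the data transfer: "On-Site Study Coordinator will abstract chart information onto case report form". The third concerns safety reporting: "Adverse events will be determined from patient charts and reported within 7 days". The last has the completed paperwork sent on to the research coordinator.
- **Consent and Randomization.** The on-site coordinator obtains consent and then allocates: "On-Site Study Coordinator will determine randomization assignment of each participant the day of procedure after having consented the participant". The notebook is divided by EP, gender and procedure type. It shows a number and not a drug: "Treatment assignment number will be listed to the right of SSN". The drug itself is concealed: "The treatment assignment number correlates to an envelope with the treatment assignment sealed within to be brought to the BHVH pharmacy". Pharmacy staff alone may open that envelope.
- **Study Design (item 4).** Pharmacy draws up two clear solutions of equal volume (10 cc). The surgeon is the only person said to be blinded. Volume given is to be collected for each patient. Enrollment runs from 11/03/2008 to 08/30/2012.
- **Treatment Preparation, EP nursing staff.** The nurse hands over a pre-drawn syringe and charts a generic term for the anesthetic, with the dosage, following usual practice.
- **Treatment verification and continued monitoring, Research coordinator.** A different role checks each day that the randomization number received the correct study medication.

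**The concern.** The sealed envelope and the generic chart entry keep the drug identity away from the people around the patient, including the person who enrolls. The first post-surgery bullet then sends that same person to find out what was given. The look-up comes after each patient's operation, but enrollment lasts several years, so anything learned would accumulate while later patients are still being approached and earlier charts are still being abstracted.

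At stake is the neutrality of the steps where the abstractor uses judgment. Item 3 of the protocol says that all data come from patient charts, and this role transfers them to the case report form. Someone who knows the arm may, without intending to, resolve an ambiguous chart entry differently in one arm than in the other.

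**Working it through.** The plan gives no figure on this point, so the check sets the relevant texts against each other.

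**1. Do the duties meet in one role?** Yes. Consent and allocation are assigned to the on-site coordinator under Consent and Randomization. The anesthetic look-up, chart abstraction and adverse event review are listed for the same role under Data abstraction and adverse event monitoring.

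**2. Is this role meant to be masked?** This is implied and not stated. The notebook shows only a number and the envelope is for pharmacy alone, so the coordinator is not meant to see the drug before treatment. No sentence says that the coordinator stays masked afterwards.

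**3. What would the look-up reveal?** The documents never describe the EP lab records, which leaves two cases:

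| EP lab records contain | Consequence |
|---|---|
| The name of the study drug | The person who enrolls and abstracts is unmasked, patient by patient, during accrual |
| Only the generic term and dosage that nurses are told to chart | The study drug cannot be identified from them, so the bullet cannot be carried out as worded |

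In either case the envelope rule, the nursing entry and the look-up bullet need to be made consistent.

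**4. Is there a legitimate need for the look-up?** Yes. Volume given is a required data item. The surgeon may give supplemental local anesthetic, which must be documented in the Apollo report. Under Surgical Procedure, Anesthesiologist, use of agents outside the requested regimen matters for eligibility: "local anesthetics like mepivacaine could disqualify the patient". All three can be recorded without naming what was in the study syringe.

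**5. Does anyone else already check identity?** Yes. The research coordinator receives the forms and verifies the medication against the randomization number. That step does not require the on-site coordinator to know the drug.

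**6. Which data are exposed?**

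| Item | Who generates it | Discretion left to the abstractor |
|---|---|---|
| Pain scores | EP nursing staff, under standard protocol | Little in copying; some in choosing which score stands for 4-24 hours |
| Narcotic type, number and dose | Chart entries | Little |
| Patient movement during implantation | Read from the chart | Some; no definition is given |
| Adverse events | Determined from charts | Some; not a listed primary or secondary outcome |

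**The case against.** The strongest reply is that nothing shows the EP lab records name the drug. Pharmacy alone opens the envelope, the two solutions look alike, the syringe arrives pre-drawn, and nurses chart a generic term. No step describes how the drug name would reach those records. The bullet may also be loose wording for volume, supplemental doses or off-protocol agents. Both points are fair, and they are why this is a conditional risk. They do not settle the matter: the nursing instruction concerns the patient's chart and leaves usual practice undefined, and the bullet does not limit itself to volume or supplements. If the narrower meaning was intended, the rewording below states it.

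The objection is also right against three stronger readings that a reader might infer:

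- *That the plan breaks its own blinding.* It does not. Only the surgeon is declared blinded, and a post-surgery look-up does not undo concealment for the same patient, who consented before the notebook was used.
- *That the pain scores are biased at source.* Nurses record them, and the abstractor mostly copies.
- *That the coordinator could predict later assignments.* The notebook lists patients in order within strata, but the documents do not say whether the lists are blocked or how. Any prediction rate would rest wholly on assumed blocking and assumed knowledge.

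Finally, two of the three discretionary steps exist because the 4-24 hour score and patient movement are not tightly defined. Masking reduces the harm from those gaps but does not close them.

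**Conclusion.** The concern holds as a conditional masking risk. It rests on a stated instruction, not on missing detail alone: the role that enrolls, randomizes and abstracts is told to determine the anesthetic given. Unmasking follows only if the EP lab records identify the study drug, which cannot be established from the documents. If they do not, the instruction cannot identify the study drug and still needs correcting.

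The size cannot be derived. Any bias would be confined to the choice of the 4-24 hour pain score, the reading of patient movement, and adverse event determination. This is a cheap improvement of low to moderate priority, not a flaw that undermines the comparison.

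**What to change.** Under Data abstraction and adverse event monitoring, reword the coordinator's first bullet so that the on-site coordinator:

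- copies the treatment assignment number from the randomization notebook onto the form (no section places that number in the EP lab records or the Apollo report);
- records from the EP lab records and Apollo report only the volume of masked study solution given and any supplemental or off-protocol local anesthetic;
- does not record or seek the identity of the study drug.

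Add two statements: that EP lab entries for the study syringe use the same generic wording that nurses use in the chart, and that the on-site coordinator stays masked to assignment while enrolling and abstracting.

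Leave the identity check with the research coordinator, and name the source: the assignment number is linked to the pharmacy's opened envelope or dispensing information. The protocol does not currently say what that check is made against.

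**Cost.** One bullet reworded, two sentences added and one source named; no dose or clinical rule changes. The research coordinator must obtain the identity from pharmacy within the daily verification already planned. The downside is that drug identity leaves the on-site form. The check then shows what was dispensed for that number, and administration is confirmed only by the masked syringe entry.
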